13.4.2. Reporting Adverse Events to the Responsible IEC/IRB and Health Authorities

Adverse events that meet the IEC/IRB requirements for reporting must be reported within the IEC/IRB's written guidelines. Each clinical site will refer to and follow any guidelines set forth by their Approving IEC/IRB. Each clinical site will refer to and follow any guidelines set forth by their local governing Health Authorities.

The Sponsor will report applicable Adverse Events to the local health authorities according the written guidelines, including reporting timelines.

13.4.3. Event of Special Interest

None

13.5. Reporting of Pregnancy

Subjects reporting pregnancy (by self-report) during the study will be discontinued after the event is recorded as an Adverse Event. Once discontinued, pregnant participants and their fetuses will not be monitored for study related purposes. Pregnant participants are not discontinued from contact lens or solution related studies for safety concerns, but due to general concerns relating to pregnancy and contact lens use. Specifically, pregnant women are discontinued due to fluctuations in refractive error and/or visual acuity that occur secondary to systemic hormonal changes, and not due to unforeseen health risks to the mother or fetus.

14. STATISTICAL METHODS

14.1. General Considerations

Statistical Analysis will be undertaken by the sponsor or under the authority of the sponsor. A general description of the statistical methods to be implemented in this clinical trial is outlined below.

All data summaries and statistical analyses will be performed using the SAS software Version 9.4 or higher (SAS Institute, Cary, NC). Throughout the analysis of data, the results for each subject/eye will be used when available for summarization and statistical analysis. Unscheduled visits will be summarized separately and will be excluded from the statistical analysis.

Summary tables (descriptive statistics and/or frequency tables) will be provided for all baseline variables, efficacy variables and safety variables as appropriate. Continuous variables will be summarized with descriptive statistics (n, mean, standard deviation [SD], median, minimum and maximum). Frequency count and percentage of subjects or eyes within each category will be provided for categorical data.

14.2. Sample Size Justification

The plan is to enroll 130 subjects with a target completion of 120 subjects. This is a feasibility study and the sample size is chosen by the study responsible clinician and was not based on

Clinical Study Protocol

Johnson & Johnson Vision Care, Inc.

any statistical power analysis. The data collected for this study will be used to design future clinical trials. However, power calculation was conducted under different scenarios for the primary hypothesis testing to provide estimates on power with 120 subjects and both CLUE comfort and vision will be tested with 2-sided type I error of 0.05.

Table 6 provides a summary of power based on the hypothesis of non-inferiority for either CLUE comfort or vision score with 120 subjects to complete the study and two-sided Type I error of 0.05 with the assumptions for treatment effect (Test – Control) of CLUE score, standard deviation and intraclass correlation. The power calculation was conducted using the POWER procedure in SAS 9.4.

Table 6: Power Calculation for the Primary Hypothesis of either CLUE comfort or vision score (Non-inferiority) with Type I error of 0.05.

Mean Difference (Test - Control)	Standard Deviation	Total Sample Size (n/2 per sequence)	Intraclass Correlation			
			0.4	0.5	0.6	0.7
0	21	120	0.765	0.829	0.895	0.956
0	23	120	0.697	0.765	0.842	0.921
0	25	120	0.634	0.703	0.785	0.878
0	27	120	0.578	0.645	0.729	0.831
1	21	120	0.884	0.929	0.967	0.991
1	23	120	0.829	0.884	0.937	0.978
1	25	120	0.771	0.834	0.899	0.958
1	27	120	0.765	0.829	0.895	0.956

As shown in the Table 6, the study will be powered (power of 0.8 or higher) to show non-inferiority of the Test lens compared to the Control lens with respect to either CLUE comfort or vision score for the following scenarios: 1) the mean difference ≥ 0 , the standard deviation and an intraclass correlation ≥ 0.7 . 2) the mean difference ≥ 0 , the standard deviation ≤ 23 and an intraclass correlation ≥ 0.6 . 3) the mean difference ≥ 0 , the standard deviation ≤ 21 and an intraclass correlation ≥ 0.5 . 4) the mean difference ≥ 1 , the standard deviation ≤ 23 and an intraclass correlation ≥ 0.4 . 5) the mean difference ≥ 1 , the standard deviation ≤ 27 and an intraclass correlation ≥ 0.5 .

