14.5. Primary Analysis

The co-primary endpoints for this study are the CLUE comfort and the CLUE vision scores evaluated after 7 ± 2 days of lens wear. The primary analysis will be conducted on per-protocol and ITT populations.

CLUE Comfort and Vision scores

CLUE comfort and vision scores after 7 ± 2 days of lens wear will be analyzed separately using a linear mixed effect model to compare between Test and Control lenses. Each regression model will include the baseline score, lens type, lens wearing sequence and lens wearing period as fixed effects and investigational site as a random effect (G-side). Other subject characteristics such as habitual lens, age, gender and will also be included as fixed effects when appropriate. The habitual lens will be categorized as ACUVUE OASYS 1-DAY, silicone hydrogel daily disposable – non-ACUVUE OASYS 1-DAY and non-silicone hydrogel daily disposable. The covariance of residual errors between different periods for the same subject will be modeled using either homogenous compound symmetry (CS), First-Order Ante-dependence (ANTE) or unstructured (UN) covariance structure. The structure that returns the lowest finite sample corrected Akaike's Information criterion⁷ will be selected as the structure that best fits the model. The Kenward and Roger method will be used for the calculation of the denominator degree of freedom.⁸

The null and alternative hypotheses for non-inferiority of Test lens relative to Control are as follows:

$$H_0: \Delta < -5$$
$$H_A: \Delta \geq -5$$

where Δ is the CLUE score mean difference after 7 ± 2 days of lens wear between Test lens and Control lens (Test minus Control). The hypothesis will be tested via the corresponding two-sided 95% confidence interval (CI) for least squares mean (LSM) difference (Test - Control) in CLUE scores. Non-inferiority will be declared if the lower bound of the confidence interval

Clinical Study Protocol

Johnson & Johnson Vision Care, Inc.

of the mean difference between Test and Control is greater than -5. If non-inferiority is demonstrated, superiority will be tested and concluded if the lower bound of the 95% CI is greater than 0.

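### Table 6 was calculated at one-sided alpha 0.05, not the stated two-sided 0.05, so the claimed regions of power 0.8 or higher are too wide

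*Combined protocol and SAP*

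**What the plan says.** Section 14.2 gives the alpha level in two places. The first concerns the tests: "both CLUE comfort and vision will be tested with 2-sided type I error of 0.05". The second concerns the power table, which is described as calculated "with 120 subjects to complete the study and two-sided Type I error of 0.05 with the assumptions for treatment effect". The title of Table 6 gives 0.05 without saying whether it is one-sided or two-sided.

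Section 14.5 sets the decision rule: "The hypothesis will be tested via the corresponding two-sided 95% confidence interval (CI) for least squares mean (LSM) difference". Non-inferiority is declared when the lower limit exceeds -5.

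From Table 6, section 14.2 concludes that "the study will be powered (power of 0.8 or higher) to show non-inferiority of the Test lens compared to the Control lens" in five scenarios, each a region of mean difference, SD and intraclass correlation (ICC). The first has a gap where the SD limit should be: "the standard deviation and an intraclass correlation". Section 14.2 also says that the clinician chose the sample size and that it does not rest on a power calculation.

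**The concern.** Declaring non-inferiority from the lower limit of a two-sided 95% interval spends 0.025 in the one direction that matters. Power for that rule, and for the alpha stated in section 14.2, must therefore be computed at one-sided 0.025. If 0.05 was entered as the one-sided level, every figure is too high.

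At stake is the list of scenarios for which the protocol claims power of at least 0.8. Someone interpreting a missed margin, or using this study to plan the next one as section 14.2 intends, would take the chance of missing non-inferiority to be smaller than it is.

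**Working it through.** **Inputs.** Completers n = 120 (section 14.2). Margin 5 CLUE points (sections 2.3 and 14.5). 2×2 crossover (section 4.1). Mean differences 0 and 1, SDs 21 to 27 and ICCs 0.4 to 0.7 (Table 6). SAS PROC POWER (section 14.2).

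**Formulas** (paired non-inferiority t-test):

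- SD of the within-subject difference = SD × √(2(1 − ICC))
- SE = that value / √120
- Noncentrality = (difference + 5) / SE
- Power = probability that a noncentral t with 119 df exceeds the critical value, which is 1.658 at one-sided 0.05 and 1.980 at one-sided 0.025

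**One cell in full: difference 0, SD 21, ICC 0.5.** SD of the difference = 21 × √1 = 21. SE = 21/10.954 = 1.917. Noncentrality = 5/1.917 = 2.608. Power is 0.829 at one-sided 0.05, which is the printed figure, and 0.735 at one-sided 0.025.

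**All 32 cells.** At one-sided 0.05, 28 cells match to three decimals, with a largest gap of 0.0005. At one-sided 0.025 none match. Using 118 df gives the same 28 matches. A normal approximation does not close the gap (0.742 for the cell above), and a parallel-group formula gives only 0.26 to 0.37.

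The four unmatched cells are the row for difference 1, SD 27. It is printed as 0.765/0.829/0.895/0.956, identical to the row for difference 0, SD 21. It should read 0.714/0.781/0.856/0.931 at one-sided 0.05. This is a separate copying error.

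**Power at the stated alpha (one-sided 0.025):**

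| Difference | SD | ICC 0.4 | 0.5 | 0.6 | 0.7 |
|---|---|---|---|---|---|
| 0 | 21 | 0.656 | 0.735 | 0.824 | 0.916 |
| 0 | 23 | 0.578 | 0.656 | 0.752 | 0.862 |
| 0 | 25 | 0.510 | 0.584 | 0.681 | 0.801 |
| 0 | 27 | 0.451 | 0.521 | 0.614 | 0.738 |
| 1 | 21 | 0.809 | 0.874 | 0.935 | 0.980 |
| 1 | 23 | 0.735 | 0.809 | 0.887 | 0.955 |
| 1 | 25 | 0.663 | 0.741 | 0.830 | 0.920 |
| 1 | 27 | 0.597 | 0.675 | 0.770 | 0.876 |

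In the 28 reproduced cells the overstatement runs from 0.991 − 0.980 = 0.011 to 0.578 − 0.451 = 0.127.

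**The five scenarios at their boundaries:**

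| Scenario | Difference, SD, ICC | Printed | One-sided 0.025 | Table cells in region still ≥ 0.80 |
|---|---|---|---|---|
| 1 (SD limit inferred) | 0, 27, 0.7 | 0.831 | 0.738 | 7 of 8 |
| 2 | 0, 23, 0.6 | 0.842 | 0.752 | 7 of 8 |
| 3 | 0, 21, 0.5 | 0.829 | 0.735 | 5 of 6 |
| 4 | 1, 23, 0.4 | 0.829 | 0.735 | 7 of 8 |
| 5 (copied row) | 1, 27, 0.5 | 0.829 | 0.675 | 9 of 12 |

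Scenario 5 fails for two reasons. Its boundary cell lies in the copied row and reaches only 0.781 even at one-sided 0.05. The alpha error on its own also breaks the scenario inside its region, at (1, 25, 0.5): printed 0.834, against 0.741.

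Of the 21 cells printed at 0.80 or above, 14 remain. Five of the seven lost, (0, 21, 0.5), (0, 23, 0.6), (0, 27, 0.7), (1, 23, 0.4) and (1, 25, 0.5), are lost to alpha alone. The other two, (1, 27, 0.5) and (1, 27, 0.6), lie in the copied row.

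**The case against.** The strongest reply is that little depends on the table. The study is labelled a feasibility study, all its hypotheses are called exploratory, and the clinician set the sample size. That stands, and it limits the consequence: neither the sample size nor the decision rule is put in doubt. It does not excuse the table, because section 14.2 still makes an affirmative power claim under a stated alpha, and the claim is wrong for that alpha.

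The evidence for the five scenarios is also uneven. Only scenarios 2, 3 and 4 fail at a printed boundary through alpha alone. Scenario 1 has no printed SD limit. Reading it as SD ≤ 27 is an inference, supported by the 0.831 that Table 6 prints there. If 25 was meant, the scenario would just pass (0.801); with no limit at all it fails. Scenario 5's boundary cell combines the alpha error with the copied row, although its cell at SD 25 fails through alpha alone. Most table cells within every region stay at or above 0.80.

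Finally, the planned analysis is a mixed model with baseline score and other covariates, whose power may differ somewhat from a paired t-test. The documents do not allow that difference to be quantified, and Table 6 makes no such allowance, so it cannot account for figures that match one-sided 0.05 to three decimals.

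**Conclusion.** The concern holds. Seven of the eight rows of Table 6 were computed at one-sided 0.05, while section 14.2 states two-sided 0.05 and section 14.5 applies the equivalent of one-sided 0.025. At the boundaries of scenarios 1 to 4, and at (1, 25, 0.5) in scenario 5, the chance of missing non-inferiority is about 25% to 27%, not the 16% to 17% implied by the table.

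This rests on the table's own paired t method with 120 completers and, for scenario 1, on the inferred limit of SD 27. For difference 0 and ICC 0.7, power of 0.80 is reached only up to SD 25.0. The error is in the stated power only. It should be corrected, but it does not threaten the design.

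**What to change.** Re-run PROC POWER at one-sided alpha 0.025, replace Table 6 including the row for difference 1, SD 27, and state the sidedness in the table title. Then restate the scenarios with power of at least 0.80:

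- difference ≥ 0: SD ≤ 21 with ICC ≥ 0.6 (0.824), or SD ≤ 25 with ICC ≥ 0.7 (0.801);
- difference ≥ 1: SD ≤ 21 with ICC ≥ 0.4 (0.809), SD ≤ 23 with ICC ≥ 0.5 (0.809), SD ≤ 25 with ICC ≥ 0.6 (0.830), or SD ≤ 27 with ICC ≥ 0.7 (0.876).

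Every scenario should print its SD limit, including the first. If one-sided 0.05 was in fact intended, the wording of section 14.2 and the interval level in section 14.5 would have to change instead. The explicit two-sided wording in both sections points to correcting the table. Because both co-primary endpoints must succeed, a line on joint power with its assumed correlation would be a useful but optional addition.

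The cost is one re-run and edited text in section 14.2, with less favourable stated power. Correcting the table requires no change to the sample size or the decision rule.

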2.3. Hypotheses

This is a feasibility study and all the hypotheses are exploratory in nature.

Primary Hypotheses:

There are two co-primary hypotheses in this study. Both of them must be met to satisfy the primary objective of the study.

1. The Test lens will be non-inferior to the Control lens with respect to overall CLUE comfort score at the follow-up visit. A non-inferiority margin of -5 points will be used.

Clinical Study Protocol

Johnson & Johnson Vision Care, Inc.

2. The Test lens will be non-inferior to the Control lens with respect to overall CLUE vision score at the follow-up visit. A non-inferiority margin of -5 points will be used.

Secondary Hypotheses:

1. The Test lens will be non-inferior to the Control lens with respect to logMAR visual performance (using ETDRS visual acuity charts) at the follow-up visit. A non-inferiority margin of 0.05 logMAR will be used.
2. The Test lens will be non-inferior to the Control lens with respect to average daily wear time at 1-week follow-up visit. A non-inferiority margin of 1 hour will be used.

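### Section 14.2's power of 0.8 or higher is for one CLUE endpoint; at the limits of its five scenarios the power to pass both co-primaries is below 0.8, and Table 6 uses a looser alpha than the planned test

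*Combined protocol and SAP*

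**What the plan says.** Section 2.3 names two co-primary hypotheses, non-inferiority on CLUE comfort and on CLUE vision. For each, "A non-inferiority margin of -5 points will be used". Of the pair it says: "Both of them must be met to satisfy the primary objective of the study".

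Section 14.2 says the sample size was the clinician's choice and not the result of a power analysis. It then gives power for 120 completers in a table titled "Power Calculation for the Primary Hypothesis of either CLUE comfort or vision score", and states that "both CLUE comfort and vision will be tested with 2-sided type I error of 0.05". From the table it concludes that "the study will be powered (power of 0.8 or higher) to show non-inferiority of the Test lens compared to the Control lens". The rest of that sentence confines the claim to one score at a time. Five scenarios follow, each set by inclusive limits on mean difference, SD and intraclass correlation (ICC). No joint power is given, and no correlation between the two endpoints.

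Section 14.5 tests each endpoint through "the corresponding two-sided 95% confidence interval (CI) for least squares mean (LSM) difference". Non-inferiority needs the lower bound to lie above -5.

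**The concern.** The trial's success rule and its power statement refer to different events. Passing one endpoint does not meet the primary objective, and the chance of passing both cannot exceed the chance of passing either one. It equals the single-endpoint power only if the two results always agree. The printed values at the scenario limits are only just above 0.8, so little loss is needed to fall below it.

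The table's alpha also matters. The section states two-sided 0.05, and the confidence-interval rule in section 14.5 is equivalent to one-sided 0.025. A table computed at one-sided 0.05 overstates power for the planned test even before the second endpoint is considered.

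What is at stake is the accuracy of a published figure. Section 14.2 introduces the calculation as serving the primary hypothesis testing, and says the study's data will inform later trials.

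**Working it through.** **Inputs.** 120 completers, equal sequences, mean differences, SDs and ICCs (section 14.2, Table 6); margin -5 and the both-must-pass rule (section 2.3); two-sided 95% CI (section 14.5). The correlation r between the two estimated treatment differences is not in the documents, so I assume 0, 0.5 and 0.8. I also assume equal power on the two endpoints. For scenario 1 no SD limit is legible; I take 27, the largest SD in Table 6.

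**Single-endpoint power.** Paired non-inferiority t-test, noncentral t, 119 degrees of freedom:

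- SE = SD × √(2(1 − ICC)/120)
- noncentrality = (difference + 5)/SE
- critical t = 1.658 at one-sided 0.05, 1.980 at one-sided 0.025

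**Reproducing Table 6.** Scenario 2 limit (difference 0, SD 23, ICC 0.6): SE = 23 × √(0.8/120) = 1.878; noncentrality = 5/1.878 = 2.662. Power is 0.842 at one-sided 0.05, as printed, and 0.752 at one-sided 0.025. Across the table, 28 of 32 cells match to three decimals at one-sided 0.05.

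The four that do not match are the row for difference 1, SD 27. It prints 0.765/0.829/0.895/0.956, identical to the row for difference 0, SD 21. At one-sided 0.05 it should be 0.714/0.781/0.856/0.931. For ICC 0.5: SE = 27 × √(1/120) = 2.465; noncentrality = 6/2.465 = 2.434; power 0.781.

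**Joint power.** With single-endpoint power π and z = Φ⁻¹(π), joint power is the bivariate normal probability Φ₂(z, z; r). At r = 0 this is π²; for example 0.842² = 0.709.

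| Scenario limit (difference, SD, ICC) | Printed | Joint from printed, r = 0 / 0.5 / 0.8 | Single endpoint, one-sided 0.025 | Joint at one-sided 0.025, r = 0 / 0.5 / 0.8 |
|---|---|---|---|---|
| 1 (0, 27, 0.7) | 0.831 | 0.691 / 0.730 / 0.767 | 0.738 | 0.545 / 0.605 / 0.655 |
| 2 (0, 23, 0.6) | 0.842 | 0.709 / 0.746 / 0.781 | 0.752 | 0.566 / 0.623 / 0.672 |
| 3 (0, 21, 0.5) | 0.829 | 0.687 / 0.728 / 0.765 | 0.735 | 0.540 / 0.601 / 0.651 |
| 4 (1, 23, 0.4) | 0.829 | 0.687 / 0.728 / 0.765 | 0.735 | 0.540 / 0.601 / 0.651 |
| 5 (1, 27, 0.5) | 0.829 | 0.687 / 0.728 / 0.765 | 0.675 | 0.456 / 0.527 / 0.583 |

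The three effects separate as follows.

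- **Both-must-pass rule alone, printed values:** 0.69–0.71 at r = 0, rising to 0.77–0.78 at r = 0.8. Reaching 0.80 needs r of about 0.90 (scenario 2) to 0.96 (scenarios 3 to 5).
- **Duplicated row, at Table 6's own alpha:** scenario 5 falls to 0.781 for one endpoint, and to 0.610 / 0.661 / 0.706 jointly.
- **Alpha:** under the planned CI rule each limit is below 0.80 for a single endpoint, so joint power is below 0.80 at any r.

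**Inside the regions.** With r = 0, joint power of 0.80 needs single-endpoint power of √0.80 = 0.894. Of the 21 printed cells at or above 0.80, 12 keep joint power of at least 0.80 at r = 0, 14 at r = 0.5 and 15 at r = 0.8. At one-sided 0.025 the counts over all 32 cells are 5 (one with difference 0, four with difference 1), 6 and 9.

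**The case against.** **The limitation is disclosed.** Section 14.2 says "with respect to either CLUE comfort or vision score for the following scenarios", and the table title says the same. A reader might infer that the protocol claims 0.8 as the chance of meeting the primary objective. It does not say that. The joint figure is left out; it is not misstated. This stands. But the figure the success rule calls for is still missing, and a reader who derives it from Table 6 starts from the wrong alpha.

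**The shortfall is not uniform.** A reader might infer that the five scenarios lack 80% joint power throughout. They do not: at difference 0, SD 21, ICC 0.7 the printed 0.956 gives 0.914 jointly at r = 0, and 0.839 at one-sided 0.025. The point holds at the limits. The limits count because the scenarios are written as inclusive regions, so the 0.8 claim has to hold there.

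**Little depends on the table.** A reader might infer that 120 completers are too few, or that a sample-size derivation failed. Section 14.2 says N was not power-based, and section 2.3 calls all hypotheses exploratory. Neither inference is supported. Nor does the both-must-pass rule call for an alpha adjustment; it affects power only.

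**The correlation is unknown.** True. On the printed values the limits would reach 0.8 if r were about 0.90 to 0.96 or higher, for which the documents give no support. Under the planned CI rule the conclusion at the limits does not depend on r.

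**Scenario 1's SD limit is my assumption.** The gap may have arisen in reproducing the text. If the intended limit were 25, the printed 0.878 would give 0.771 / 0.799 / 0.827 jointly, and single-endpoint power at one-sided 0.025 would be 0.801. Scenario 1 would then be milder; the other four are unaffected.

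**Conclusion.** The point holds as a reporting defect in section 14.2. The both-must-pass rule alone takes power at the scenario limits from the printed 0.83–0.84 to 0.69–0.78 for r between 0 and 0.8. The alpha mismatch and the duplicated row are separate errors. With all three corrected, joint power at the limits is 0.46–0.57 (r = 0), 0.53–0.62 (r = 0.5) and 0.58–0.67 (r = 0.8), and single-endpoint power is 0.68–0.75.

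These figures rest on Table 6's own variance model, equal power on the two endpoints, an assumed r, and SD 27 for scenario 1. They do not allow for any precision gained from covariates in the mixed model. The finding concerns what the protocol says its power is; it does not show that the design is unsuitable for an exploratory feasibility study.

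**What to change.** Keep 120 completers and, in section 14.2:

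1. Recompute Table 6 at one-sided 0.025, to match the two-sided 95% CI in section 14.5, and label it so.
2. Correct the row for mean difference 1, SD 27. At one-sided 0.025 my calculation gives 0.597/0.675/0.770/0.876.
3. Add joint power for meeting both co-primaries at stated correlations between the two estimated treatment differences, for example 0, 0.5 and 0.8. Say that this is not the correlation between the comfort and vision scores themselves.
4. Rewrite the list of powered scenarios on joint power, and give the SD limit for scenario 1.

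The cost is one recalculated table and one reworded paragraph, with a less favourable stated power. No extra subjects, alpha adjustment or design change is needed.

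### Table 6 prints the same powers for (difference 1, SD 27) as for (difference 0, SD 21), which cannot be right, and scenario 5's claim of at least 0.80 power fails as a result

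*Combined protocol and SAP*

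**What the plan says.** Section 14.2 (Sample Size Justification) gives Table 6, the power for non-inferiority on either CLUE score with 120 completers, for mean differences of 0 and 1, SDs of 21 to 27 and ICCs of 0.4 to 0.7. The first row (difference, SD, N, then the four powers) reads "0 21 120 0.765 0.829 0.895 0.956" and the last reads "1 27 120 0.765 0.829 0.895 0.956". The row just above the last reads "1 25 120 0.771 0.834 0.899 0.958".

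The paragraph below the table names five scenarios said to have power of 0.8 or higher. The fifth is a mean difference of at least 1, with "the standard deviation ≤ 27 and an intraclass correlation ≥ 0.5".

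On alpha, the section says that "both CLUE comfort and vision will be tested with 2-sided type I error of 0.05", and introduces the table as calculated "with 120 subjects to complete the study and two-sided Type I error of 0.05". Section 14.5 (Primary Analysis) declares non-inferiority when the lower bound of a two-sided 95% confidence interval for Test minus Control exceeds -5. The margin of -5 is set in section 2.3.

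Section 14.2 also says that "the sample size is chosen by the study responsible clinician" and that no power analysis was behind it. Section 2.3 calls all hypotheses exploratory.

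**The concern.** Two different combinations of difference and SD carry the same four powers to three decimals. The neighbouring rows also suggest that the last row is wrong. At difference 0, going from SD 25 to SD 27 lowers the printed power by 0.047 to 0.058 across the four ICCs. At difference 1 the same step lowers it by only 0.002 to 0.006. This looks like a row copied from the top of the table.

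Scenario 5 depends on that row: its corner (difference 1, SD 27, ICC 0.5) is the printed 0.829. If the row is wrong, the protocol credits the study with power it does not have in that scenario. The section says the data will be used to design future trials, so a reader could carry the figure forward, or misjudge a failed non-inferiority result.

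**Working it through.** **Inputs.** Completers n = 120, each measured on both lenses (14.2). Margin -5 (2.3). Difference, SD and ICC grid from Table 6. Alpha: two-sided 0.05 as stated in 14.2. Under the lower-bound rule of 14.5 this is a one-sided 0.025 test. One-sided 0.05 was tried as the alternative.

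**Formula.** For a within-subject comparison:

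- SD of the difference = SD × √(2(1 − ICC))
- non-centrality = (difference + 5) × √120 / SD of the difference
- power = probability that a non-central t with 119 df exceeds the critical value, which is 1.658 at one-sided 0.05 and 1.980 at one-sided 0.025.

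Using 118 df changes the results by at most 0.0001.

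**Step 1: reproduce the table.** For difference 0, SD 21, ICC 0.5, the SD of the difference is 21 × √1 = 21 and the non-centrality is 5 × 10.954/21 = 2.608. Power at one-sided 0.05 is 0.829, as printed. On this basis all 28 cells of the first seven rows match to three decimals, and none of the four cells of the last row does. At one-sided 0.025, none of the 32 printed cells matches.

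**Step 2: show that the two rows cannot be equal.** At fixed n, ICC and alpha, power rises strictly with (difference + 5)/SD. The ratio is 5/21 = 0.238 in the first row and 6/27 = 0.222 in the last. Equality at difference 1 would need SD = 21 × 6/5 = 25.2, not 27. This holds at any alpha.

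**Step 3: recompute the last row.** At ICC 0.5 the SD of the difference is 27 and the non-centrality is 6 × 10.954/27 = 2.434.

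| Difference 1, SD 27 | ICC 0.4 | 0.5 | 0.6 | 0.7 |
|---|---|---|---|---|
| Printed | 0.765 | 0.829 | 0.895 | 0.956 |
| One-sided 0.05 | 0.714 | 0.781 | 0.856 | 0.931 |
| Overstated by | 0.051 | 0.048 | 0.039 | 0.025 |
| Stated alpha (one-sided 0.025) | 0.597 | 0.675 | 0.770 | 0.876 |
| Overstated by | 0.168 | 0.154 | 0.125 | 0.080 |

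A simulation of 400,000 draws at ICC 0.5 also gave 0.781 and 0.675.

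**Step 4: what scenario 5 would need for power 0.80.**

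| | One-sided 0.05 | Stated alpha |
|---|---|---|
| Largest SD at difference 1, ICC 0.5 | 26.3 | 23.3 |
| Smallest ICC at difference 1, SD 27 | 0.526 | 0.629 |
| Completers at difference 1, SD 27, ICC 0.5 | 127 | 161 |

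**Step 5: the other scenarios.** Corners at one-sided 0.05, then at the stated alpha:

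- Scenario 1 (0, 27, 0.7): 0.831, 0.738. The text shows no SD limit here, so the table's maximum of 27 is assumed.
- Scenario 2 (0, 23, 0.6): 0.842, 0.752.
- Scenario 3 (0, 21, 0.5): 0.829, 0.735.
- Scenario 4 (1, 23, 0.4): 0.829, 0.735.

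Cells at 0.80 or more number 21 as printed, 20 at one-sided 0.05 and 14 at the stated alpha.

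**The case against.** The strongest reply is that two defects are being combined. The repeated row alone costs 0.048 at scenario 5's corner (0.829 against 0.781). The further fall to 0.675, a difference of 0.106, comes from the mismatch between the one-sided 0.05 that reproduces the table and the two-sided 0.05 that the text states. That is a fair separation, and it is why both bases are shown. It does not rescue scenario 5, which misses 0.80 even on the basis more favourable to the sponsor. The alpha mismatch still matters for the repair, because correcting four cells would leave scenario text that is untrue for the planned test.

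The table's caption gives a type I error of 0.05 without saying one- or two-sided. This is weak mitigation, since the sentence introducing the table says two-sided and section 14.5 uses a two-sided 95% interval.

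The planned analysis is a mixed model with baseline score and other covariates, whereas this calculation is an unadjusted paired t. That limit stands: 0.675 is Table 6's own calculation at the stated alpha, not the exact power of the section 14.5 model. The impossibility of the repeated row does not depend on it.

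Finally, little follows in practice. The sample size was not chosen from this table, SD 27 is the edge of the grid, and on the one-sided 0.05 basis only one cell crosses 0.80. That is correct and limits the weight of the point. It does not make the stated power right.

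**Conclusion.** The point holds, as a minor one. The (difference 1, SD 27) row of Table 6 is wrong, and scenario 5's claim of power of at least 0.80 is false at its corner: 0.781 on the one-sided 0.05 basis that reproduces the rest of the table, and 0.675 at the stated alpha, against 0.829 printed. Both figures assume a paired t-test with 120 completers, a margin of -5 and a common SD on the two lenses. This is an error in a stated power, not a fault in the design.

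**What to change.** Rerun Table 6 for the test in section 14.5 (lower bound of a two-sided 95% interval, one-sided 0.025). The last row becomes 0.597/0.675/0.770/0.876. Then restate all the scenarios from the rerun table. At that alpha, power is at least 0.80 for:

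- difference ≥ 1 with SD ≤ 21 and ICC ≥ 0.4 (0.809), SD ≤ 23 and ICC ≥ 0.5 (0.809), SD ≤ 25 and ICC ≥ 0.6 (0.830), or SD ≤ 27 and ICC ≥ 0.7 (0.876)
- difference ≥ 0 with SD ≤ 21 and ICC ≥ 0.6 (0.824), or SD ≤ 25 and ICC ≥ 0.7 (0.801).

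Give scenario 1 an explicit SD limit.

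If the sponsor prefers to keep one-sided 0.05, label the table so and say that it differs from the test in section 14.5. Print 0.714/0.781/0.856/0.931 in the last row, and limit scenario 5 to SD ≤ 25 with ICC ≥ 0.5 (0.834) or SD ≤ 27 with ICC ≥ 0.6 (0.856). At the stated alpha these two corners are only 0.741 and 0.770, so they hold only under that label.

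The cost is one run of 32 cells and one rewritten paragraph. Sample size, conduct and decision rule stay as they are.
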